**LIST OF ABBREVIATIONS**

AE	adverse event
CBC	Complete blood count
CFR	Code of Federal Regulations
CRF	case report form
DMC	Data Monitoring Committee
DSMB	Data Safety Monitoring Board
FDA	Food and Drug Administration
FEV1	forced expiratory volume over one second
FVC	forced vital capacity
GCP	Good Clinical Practice
HIPAA	Health Insurance Portability and Accountability Act of 1996
ICF	informed consent form
ICH	International Conference on Harmonisation
IEC	Independent Ethics Committee
IRB	Institutional Review Board
NAC	n-acetylcysteine
PI	Principal Investigator
SAE	serious adverse experience

## PROTOCOL SYNOPSIS

TITLE	The Effect of NAC on Lung Function and CT Mucus Score
SPONSOR	[name], MSc
FUNDING ORGANIZATION	National Institutes of Health, Departmental funds, Division of Pulmonary and Critical Care Medicine, Department of Medicine, UCSF
RESEARCH SITES	University of California, San Francisco and University of California, Davis
RATIONALE	
Mucus plugging of the airway is consistently found in fatal and near-fatal asthma. The role of mucus as a cause of airflow obstruction in acute severe asthma suggests that mucus plays a role in the pathophysiology of airflow obstruction in chronic severe asthma as well. This role has been hard to prove, however, in large part because of difficulty in showing that mucus occludes the lumen in chronic severe disease. Using a novel approach of scoring mucus occlusion, we have used CT imaging to uncover that a majority of asthmatics in the NHLBI Severe Asthma Research Program (SARP) have at least one lung segment with a mucus plug and 27% have more than four lung segments with mucus plugs.
 
Historically, studies of mucolytics, like n-acetylcystine (NAC), have not shown benefit in other obstructive lung diseases, like COPD. However, utilizing CT mucus scores as a biomarker, we believe that mucolytic treatment may prove useful for those with significant mucus impaction.

STUDY DESIGN	This is a multi-center, randomized, double-blind, placebo-controlled phase 4 study.
PRIMARY OBJECTIVE	The primary objective is to determine if inhaled NAC decreases mucus plugs and improves lung function in patients with asthma.
SECONDARY OBJECTIVES	The secondary objective is to determine the duration of benefit of inhaled NAC in asthma.
NUMBER OF PARTICIPANTS	36
PARTICIPANT SELECTION CRITERIA	
Inclusion Criteria
 
 
1. Male or female between the ages of 18 and 80 years of age at Visit 1
 
2. Written informed consent obtained from subject and ability for subject to comply with the requirements of the study.
 
3. Able to perform reproducible spirometry according to ATS criteria
 
4. Physiological evidence of airflow obstruction (FEV1 bronchodilator reversibility of <math>\geq 12\%</math> or hyperreactivity to methacholine reflected by a methacholine PC20 <math>\leq 16</math> mg/mL) Historical methacholine data may be allowed. An exception will be made for enrollees whose FEV1 is <math>< 50\%</math> predicted (precluding methacholine challenge testing. If
 

	
bronchodilator reversibility is <12% in these participants, a diagnosis of asthma acceptable to the investigator is sufficient for inclusion in ENACT.
 
5. Clinical history of asthma per patient report or medical record
 
6. Pre-bronchodilator FEV1 > 35% predicted
 
7. Post-bronchodilator FEV1 > 40% but < 90% predicted. If the participant has past evidence of mucus impaction as described by a radiologist on a prior chest CT scan, then post-bronchodilator FEV1 needs to be >40% but <95% predicted.
 
8. Asthma requiring treatment with inhaled corticosteroids (ICS) for 3 months or greater.
 
9. CT mucus score <math>\geq 5</math>
 
10. Ability to tolerate study drug reflected by a post-treatment FEV1 <math>\geq 80\%</math> of pre- treatment, pre-bronchodilator FEV1
 
Exclusion Criteria
 
1. Pregnant, breastfeeding, or unwilling to practice birth control during participation in the study
 
2. Presence of a condition or abnormality that in the opinion of the Investigator would compromise the safety of the patient or the quality of the data
 
3. Smoking of tobacco or other recreational inhalants in last year and/or >10 pack-year smoking history
 
4. Current participation in an investigational drug trial
 
5. Uncontrolled asthma as evidenced by an asthma exacerbation in 6 weeks prior to study participation or albuterol use greater than 8 puffs per day
 
6. Other chronic pulmonary disorders, including (but not limited to) cystic fibrosis, chronic obstructive pulmonary disease, chronic bronchitis, vocal cord dysfunction (that is the sole cause of respiratory symptoms and at the PI's discretion), severe scoliosis or chest wall deformities that affect lung function, or congenital disorders of the lungs or airways
 
7. Unwillingness to follow study procedures
 
8. History of allergy or intolerance to study drug
 
9. Any other criteria that places the subject at unnecessary risk according to the judgment of the Principal Investigator

TEST PRODUCT, DOSE, AND ROUTE OF ADMINISTRATION	
10% NAC (3 ml) and 2.5 mg albuterol (0.5 ml)
 
Product will be administered every 8-12 hours (2 times per day) for 14 days. Medication will be administered via a portable nebulizer.

CONTROL PRODUCT, DOSE AND ROUTE OF ADMINISTRATION	
0.9% saline (3mL) and 2.5 mg albuterol (0.5ml)
 
Product will be administered every 8-12hours (2 times per day) for 14 days. Medication will be administered via a portable nebulizer.

DURATION OF PARTICIPATION AND DURATION OF STUDY	
Participants will be enrolled in the study up to 178 days:
 
Screening: up to 90 days
 
Treatment Period 1: 14 days
 
Washout: 60 days
 
Treatment Period 2: 14 days
 
The total duration of the study is expected to be 24 months.
 
Participant recruitment will happen on a rolling basis.

CONCOMITANT MEDICATIONS	
Prohibited:
 
 
• thiols and thiol derivatives
 
• activated charcoal
 
• inhaled insulin
 

EFFICACY EVALUATIONS	
PRIMARY ENDPOINT	The primary outcome is the % change in FEV1 from the start to the end of the treatment period (either placebo or 10% NAC).
SECONDARY ENDPOINTS	
Secondary efficacy endpoints include:
 
 
• CT mucus score
 
• FVC
 
• PEF (AM and PM)
 
• Air trapping (RV/TLC ratio)
 
• FeNO
 
• Blood eosinophils
 

OTHER EVALUATIONS	Rheological properties of sputum.
SAFETY EVALUATIONS	Incidence of adverse events
PLANNED INTERIM ANALYSES	
No interim analysis is planned
 
Serious adverse events will be monitored by the ACRC data safety monitoring committee on an ongoing basis throughout the study.

STATISTICS Primary Analysis Plan	The primary outcome is the % change in FEV1 from the start to the end of the treatment period (either placebo or 10% NAC). The first analysis will be to test the assumption of negligible carryover effects from study period 1 to period 2. We will compare the sum of the outcome values measured in the two periods for each participant across the 2 sequence groups (placebo-10% vs. 10%-placebo) using an unpaired t-test. After no or negligible carryover effect has been confirmed, we will test for the difference in treatment effects between placebo and 10% NAC using a paired t-test.
Rationale for Number of Participants	The primary goal of this study is to assess whether N-acetyl cysteine improves FEV1 after a 2-week treatment period in patients with asthma when compared to a two week treatment period of placebo. The study has a cross-over design which reduces the sample size. With help from [name]., biostatistician at Penn State, who has access to 2-week FEV1 data in NIH network trials and cohort studies in asthma that UCSF has participated in, we calculate a sample size of 36

	patients. This sample size is obtained when we factor in an effect size of 5% improvement in FEV1, a standard deviation for change in FEV1 of 20%, a within patient correlation for repeated measures of FEV1 of 0.9, and a power of 90%.
--	---

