## 7 STUDY TREATMENTS

### 7.1 Method of Assigning Participants to Treatment Groups

Up to 36 eligible patients will be randomly assigned to receive either the experimental treatment (10% NAC) or the placebo treatment (0.9% saline) during period 1 in a 1:1 ratio using a SAS-based computer-generated randomization scheme accessed by the investigational pharmacist. The UCSF investigational pharmacist will complete a randomization worksheet and log the group assignment for subjects enrolled at both UCSF and UC Davis. The UCSF investigational pharmacist will contact the UC Davis pharmacist by email or phone to inform them of the randomization. The randomization log will be shared with investigators upon study completion or in the event of a serious safety concern.

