### 14.6 Sample Size

We propose a sample size of 36, which will provide us with the power to examine the effect of NAC in a subgroup of individuals with asthma who have CT evidence of intraluminal mucus and to identify the CT mucus score that performs best as a biomarker of treatment response to NAC. Participants will be enrolled if their CT mucus scores are  $\geq 5.0$ . The sample size is obtained when we factor in an effect size of 5% improvement in FEV1, a standard deviation for change in FEV1 of 20%, a within patient correlation for repeated measures of FEV1 of 0.9, and a power of 90%.

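### The synopsis makes the primary treatment test wait on a carryover pre-test that cannot confirm absence of carryover and that costs power

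*Combined protocol and SAP*

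**What the plan says.** The Statistics row of the Protocol Synopsis (Primary Analysis Plan) sets out two steps. The first is the carryover test: "The first analysis will be to test the assumption of negligible carryover effects from study period 1 to period 2". The method is an unpaired t-test: "We will compare the sum of the outcome values measured in the two periods for each participant across the 2 sequence groups". The second is the paired t-test of placebo against 10% NAC, which is introduced by "After no or negligible carryover effect has been confirmed". The synopsis gives no significance level for the first step, no margin that would define negligible, and no analysis for the case where the first step is significant.

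Section 14.3 names a paired t-test of the % change in FEV1 as the primary analysis and mentions no pre-test. Section 14 says that a detailed SAP, including any modifications, will be written before the final data are analysed. Section 14.6 gives the size of the trial: "We propose a sample size of 36", based on "an effect size of 5% improvement in FEV1, a standard deviation for change in FEV1 of 20" per cent, and "a within patient correlation for repeated measures of FEV1 of 0.9, and a power of 90" per cent. The same 90% appears in the synopsis rationale and in Section 5.1. Section 7.1 allocates patients "in a 1:1 ratio using a SAS-based computer-generated randomization scheme".

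**The concern.** The treatment comparison is made within patients, and that is why 36 patients can be enough. The carryover comparison is made between patients on the sum of their two outcomes, so it carries all of the between-patient variation that the crossover removes. A test that weak will usually be non-significant whether or not carryover matters, and the synopsis would then report negligible carryover as confirmed.

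The reverse case is also a problem. When the pre-test is significant by chance, the trial has no stated primary analysis. The power quoted in Section 14.6 belongs to the paired t-test run alone, not to the two-step procedure in the synopsis.

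**Working it through.** **Inputs.** N = 36, effect 5 points, SD 20, correlation ρ = 0.9 and power 90% (Section 14.6); 1:1 allocation, so 18 per sequence (Section 7.1). Assumed because not stated: two-sided 0.05 for the treatment test, and 0.05 or 0.10 for the pre-test.

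**1. Reproduce the 36.** Apply ρ to the % changes in the two periods. The SD of the within-patient difference is 20 × √(2 × (1 − 0.9)) = 8.944.
- Normal approximation: (1.960 + 1.282)² × 8.944² / 5² = 33.6, so 34.
- Noncentral t: 36 patients, power 90.3% (35 give 89.5%).
- One-sided 0.05 gives 28 or 29, which does not match.

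The plan's figure is therefore reproduced with a two-sided 0.05 paired t-test and no gate.

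**2. Power of the pre-test on the same inputs.**
- SD of a patient's sum: 20 × √(2 × (1 + 0.9)) = 38.99.
- Standard error of the sequence contrast: 38.99 × √(2/18) = 13.0.
- 95% confidence interval half-width on 34 degrees of freedom: about 26 points.

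| True carryover (points) | Power, level 0.05 | Power, level 0.10 |
|---|---|---|
| 2.5 | 5.4% | 10.6% |
| 5 (the whole planned effect) | 6.6% | 12.4% |
| 10 | 11.6% | 19.5% |
| 20 | 32% | 45% |

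Power of 80% at level 0.05 needs a carryover of about 37.5 points. With SD 20 and a lower correlation between periods, power for 5 points at level 0.05 is still only 7.1% (ρ = 0.5) or 8.1% (ρ = 0).

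**3. Error rate and power of the procedure as written.** Take a non-significant pre-test as confirmation, with no fallback and no true carryover. For a patient with outcomes Y1 and Y2 of equal variance, Cov(Y1 + Y2, Y1 − Y2) = Var(Y1) − Var(Y2) = 0. Under normality and balanced sequences, the pre-test and the paired test are then independent, so the gate simply multiplies:
- Type I error: 0.05 × 0.95 = 4.75% (pre-test 0.05), or 0.05 × 0.90 = 4.5% (pre-test 0.10).
- Power: 90.3% × 0.95 = 85.8%, or 90.3% × 0.90 = 81.3%.

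Simulation (200,000 trials per setting) agrees. Type I error is 4.7% to 4.8% at pre-test 0.05 and 4.5% at 0.10, over ρ = 0, 0.5 and 0.9. It is 5.0% among trials that pass the gate. Power at pre-test 0.05 is 85.7%.

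**4. If carryover is real.** A carryover λ in the second period of the NAC-first sequence shifts the expected paired difference from τ to τ − λ/2. With τ = 5 and λ = 5 the expected difference is 2.5. The ungated paired test then has 34% power, and the pre-test flags the problem in only 6.7% of trials.

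**5. Hypothetical only: a period-1 fallback.** Suppose a period-1-only unpaired t-test were used after a significant pre-test. Overall type I error would then be:

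| ρ | Pre-test 0.05 | Pre-test 0.10 |
|---|---|---|
| 0 | 6.4% | 6.9% |
| 0.5 | 7.4% | 8.2% |
| 0.9 | 8.7% | 9.4% |

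Given a significant pre-test, that fallback would reject a true null in 24% to 79% of trials, because period-1 outcomes are correlated with the sums.

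**The case against.** A reader who knows the usual two-stage crossover analysis might infer that this plan inflates the type I error above 5%. The documents do not support that. The inflation comes from the period-1 fallback, and no section contains one. As written, the gate can only withhold a rejection, so the procedure is slightly conservative. Nor does the gate add false positives when carryover is real. With τ = 0 and λ = 5, the paired test rejects in 34% of trials without the gate and 32% with it. That is bias in the paired test itself, and the gate barely changes it.

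Two further points can be made for the plan. First, Section 14.3 has no gate and the SAP is still to be written, so the stopped branch is undefined rather than fixed in an invalid form. That is true, but it leaves two descriptions of the primary analysis in one document, and an undefined branch invites a choice made after seeing the data.

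Second, the pre-test does better on another reading of the inputs. If 20% is the SD of FEV1 level and changes in the two periods are independent, the SD of a change is 8.944 and the SD of the sum is 8.944 × √2 = 12.65. Power for 5 points is then 21% at level 0.05 and 32% at 0.10. But Section 14.6 calls the 20% an SD for change, and on this reading the paired test has only about 63% power at 36 patients. It does not reproduce the plan's sample size, and even 32% would not confirm absence.

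**Conclusion.** The condition is unsound and should go. On the inputs that reproduce the plan's 36, the pre-test has 6.6% power (level 0.05) or 12.4% (level 0.10) for a carryover equal to the planned effect, so passing it is not evidence that carryover is negligible. When there is no carryover, it removes the primary comparison from 5% or 10% of trials and lowers power from 90% to about 86% or 81%.

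The damage in the plan as written is to power and to the definition of the primary analysis, not to the false-positive rate, which stays at about 4.5% to 4.8%. The range of 6.4% to 9.4% is a warning about how the stopped branch might later be filled.

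These figures assume normal outcomes with equal variances in the two periods, 18 per sequence, a two-sided 0.05 treatment test, and non-significance taken as confirmation. If confirmation meant an interval lying inside a margin, a half-width of about 26 points would make the gate close to impassable for any margin of practical interest.

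**What to change.** - In the synopsis, delete the carryover pre-test and the clause that makes the treatment test wait for it. State one unconditional crossover comparison of NAC with placebo at a stated two-sided level, and make Section 14.3 and the SAP say the same.
- Base the assumption of negligible carryover on the planned washout. The documents give its length in more than one way: 60 days in the synopsis, 8 weeks in Section 4.1, and 84 − 21 = 63 days from Visit 6 to Visit 8 in Section 9. These need to be reconciled.
- Report the carryover estimate with its confidence interval, and pre-dose FEV1 at Visit 8 against Visit 4 by sequence, as description only. Both measurements are already scheduled (Sections 9.5 and 9.10).
- Label any period-1-only result as a sensitivity analysis that cannot replace the primary result.

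The cost is wording in the synopsis, Section 14.3 and the SAP, with no added visits, data or patients. On the plan's assumptions it restores the stated 90% power at a 5.0% type I error. It does not remove the bias that a real carryover would cause; that protection has to come from the washout, and the pre-test did not provide it either.

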## 1 BACKGROUND

Mucus plugging of the airway is consistently found in fatal asthma. Decades ago, Dunnill provided graphic descriptions in 20 cases of fatal asthma noting that "the cut surface of the lung showed a striking picture with numerous grey, glistening, mucous plugs scattered throughout the airway passages." He summarized that "pathologically, the outstanding feature of the asthmatic lung lies in the failure of clearance of the bronchial secretions." Others have confirmed these findings, and it is only a small minority of asthma deaths that are not associated with airway mucus impaction.

[figure not shown]
In non-fatal or near-fatal asthma exacerbations segmental collapse of lung lobes due to luminal occlusion is common. Lavage of these cases yields abnormal mucus plugs in the form of airway casts. The combination of airway narrowing from concentric smooth muscle contraction with luminal obstruction by mucus marks asthma as uniquely dangerous among airway diseases in its propensity for sudden and sometimes fatal exacerbations. The role of mucus as a cause of airflow obstruction in acute severe asthma suggests that mucus plays a role in the pathophysiology of airflow obstruction in chronic severe asthma as well. This role has been hard to prove, however, in large part because of difficulty in showing that mucus occludes the lumen in chronic severe disease. Lungs are available at autopsy to show mucus occlusion in fatal asthma, and it is notable that there is evidence of occlusion in asthmatics who die with asthma (rather than because of it). But

the field has yet to be persuaded of a role for mucus in airway dysfunction in chronic asthma.

[figure not shown]
### 1.1 Overview of Clinical Studies

Against this background, the preliminary data we show in Figs 1 and 2 are very important, because we show how CT lung images can reveal mucus plugs in chronic severe asthma and how these plugs are associated with lower lung function. Specifically, we use CT imaging to uncover that a majority (58%) of asthmatics in the NHLBI Severe Asthma Research Program (SARP) have at least one lung segment with a mucus plug and 27% have more than four lung segments with mucus plugs. Notably, asthmatics with a high mucus scores achieve a post albuterol FEV1 > 80% much less frequently than asthmatics who have a zero mucus score (Fig 3).

Examined another way, we find that all asthmatics with an FEV1 < 60% after albuterol treatment have abnormal mucus scores, whereas the majority of asthmatics

[figure not shown]
**Figure 1: Intraluminal mucus in CT lung images of asthmatics.** Mucus plugs in CT scan images (white arrows) were defined as complete occlusion of an airway lumen by mucus and were identified as tubular structures in longitudinal section with branching (A & B) or without branching (C) or as rounded opacities in cross-section (D). The latter were traced cephalad or caudad on adjacent slices to confirm their continuity with unoccluded bronchi (red arrow).

[figure not shown]
with an FEV1 >80% with albuterol treatment have zero or low mucus scores (Fig 3). These data clearly implicate mucus plugs in the pathogenesis of airflow obstruction in asthma. One reason why this role for mucus plugging has been underappreciated in chronic severe asthma is that mucus-related symptoms are both insensitive and non-specific indicators of mucus. This is well illustrated in the table, which presents data for the prevalence of mucus-related symptoms in asthmatics with different mucus score categories. None of the mucus-related symptoms were significantly different in the zero, low or high mucus subgroups, and it is clear that these symptoms have very limited utility to investigate the role of mucus in asthma or to identify asthmatics who might benefit from mucus-directed treatments.

## 1.2 Overview of Non-Clinical Studies

To test the hypothesis that airway mucus in asthma has abnormal elasticity, we performed rheology on induced sputum from 40 asthmatic participants recruited to UCSF as part of the SARP. The majority of these asthmatic participants (65%) had severe asthma. We compared the elastic modulus ( $G'$ ) of these participants to induced sputum  $G'$  in 11 healthy controls. We found that the  $G'$  in the asthmatic group was significantly higher than normal (Fig 4A). Notably, we found a strong inverse correlation between  $G'$  and FEV1 % (Fig 4B). This finding suggests that stiff mucus in the airway of asthmatics could be a mechanism of mucus impaction of airways and airflow obstruction. It further suggests that decreasing mucus  $G'$  could be a treatment

strategy to improve airflow. To determine if the  $G'$  of asthmatic sputum is a result of excessive mucin disulfide bridges (as it is in CF), we measured the  $G'$  in a subgroup of 6 asthmatics before and after the addition of n-Acetylcysteine (NAC) (61mM). We found that NAC markedly decreased the  $G'$  at both 2 minutes and 12 minute time-points after the addition of NAC (Fig 4A & B). This indicates that disulfide bonds are a mechanism of high sputum elasticity and a target for mucolysis in asthma, and it suggests thiol-based compounds as a rational mucolytic strategy.

**Figure 4.** A. Sputum in asthma has an increased elastic modulus ( $G'$ ). B. The  $G'$  of asthma sputum is significantly and inversely related to FEV1 (*ex vivo* data from 40 asthmatics and 11 healthy participants [red dots])

## 2 STUDY RATIONALE

Because we have shown that the high elasticity of asthmatic mucus can be markedly decreased with NAC *ex vivo* (Fig 4), we propose here an *in vivo* study to treat asthmatics with NAC to improve their lung function. It is perhaps surprising that inhaled NAC has not been tested in a clinical trial in asthma, but a significant reason has been the uncertainty outlined above for the role of mucus in chronic disease. Another factor has been that clinical trials of NAC in COPD and cystic fibrosis have had not been consistently encouraging. However, these trials have not had a biomarker to select patients who might benefit and they have used orally administered NAC, which does not achieve detectable drug concentration in airway lining fluid. Our proposal to test the efficacy of NAC in a specific patient subgroup identified by a biomarker (CT imaging) is timely and addresses a novel approach to asthma treatment. Although NAC is a suboptimal mucolytic, we are confident that high dose (10%) treatment will effectively lyse airway mucus to improve airflow and pave the way for later clinical trials of a thiol-saccharide.

